# 10. Quality assurance

### 10.1 Monitoring

The trial will have a quality control monitoring process in place to verify that all data are accurate and complete. The investigator/institution will permit trial-related monitoring, audits, REB review and regulatory inspections(s), and will provide direct access to source data/documents as required.

#### 10.2 Protocol Amendments

All protocol amendments will be reviewed and approved by the study sponsor REB.

### 10.3 Protocol Deviations

Study related procedures must be conducted in compliance with the protocol, amendments, regulations and guidelines, in order to ensure participant safety and data integrity. Any deviations from the protocol, or violations of the protocol, will be accurately documented, reported and reconciled.

Protocol deviations refer to incidents involving non-compliance with the protocol that are unlikely to have a significant impact on the participant's rights, safety or welfare, or on data integrity. Examples of deviations include: forgetting to complete a procedure at a specified visit (weight, missing lab value, etc.). If a protocol deviation occurs the following procedures will be followed:

- The local investigator or delegate will document and explain any deviation from the approved protocol
- ii) Deviations from the protocol must be reported in the CRF

Participants will not be withdrawn from the study for protocol deviations unless a criterion for discontinuation or withdrawal is met.

# 11. Trial management

# 11.1 Day-to-day management

The Ottawa Hospital Research Institute, University of Ottawa, Ottawa, Ontario, Canada is the coordinating centre for the SMART-IgAN pilot trial and is primarily responsible for the development of the trial protocol, organization of the trial, trial database, data analyses, and coordination of the trial centres.

The OHRI Project Office is responsible for the daily conduct of the trial including: data management (data validation and quality), producing and presenting reports on screening, follow-up, data quality, and outcome events, develop and communicate to trial investigators and research personnel periodic trial reports, identifying and contacting participating centres with recruitment issues, communication with investigators and research personnel regarding protocol and other procedural questions, be available to answer phone calls or emails from investigators or trial personnel to resolve any problems or questions that arise, maintenance of required documentation for regulatory agencies, preparation of presentations to the study committees, organization of Investigator meetings, and Project Office meetings with the Principal Investigator and Project Manager.

# 11.2 Site Principal Investigator and responsibilities

All participating centres will have a site PI. The site PI is responsible for ensuring compliance with respect to the intervention, visit schedule, and procedures required by the protocol. The site PI will ensure the provision of all information requested in CRF in an accurate and timely manner according to instructions provided. The site PI will maintain patient confidentiality with respect of all information accumulated in the course of the trial, other than that information to be disclosed by law.

The Site PI at each participating center is responsible for:

- 1. Obtaining ethics approval from the institutional review board or the ethics board and forwarding this to the Project Office.
- 2. Ensuring recruitment does not begin until study approval is obtained.

- 3. Ensuring the protocol is followed.
- Ensuring that an Informed Consent Form is correctly completed for each patient included in the study.
- 5. Ensuring all relevant physicians and nurses involved in the care of patients potentially eligible for the trial are aware and informed about the trial. This may involve organizing and presenting educational in-services and/or rounds about the trial.
- 6. Ensuring that potentially eligible patients are screened for the trial.
- 7. Ensuring that all enrolled patients have relevant laboratory tests obtained in accordance with the protocol.
- 8. Ensuring that all enrolled patients are followed appropriately.
- Ensuring that CRFs completed by their study staff are promptly and accurately completed and submitted to the Project Office, and that all inquiries from the Project Office regarding patient forms or other matters are addressed promptly.
- 10. Ensuring they maintain for at least 25 years after the publication of the main results, the list of patient identification numbers and patient names to enable identification of hospital records at a later date.

### 11.3 Steering committee

A Trial Steering Committee comprising of study co-investigators will be determined and will manage the overall conduct of the study. The committee will meet every 6 months via teleconference.

# 12. Analysis plan

# 12.1 Sample size justification

IgAN is the most common condition treated in the Glomerulonephritis Clinic at both sites. Approximately 30 individuals are diagnosed with IgAN on a kidney biopsy each year in Ottawa. Over the course of 2 years, we anticipate that half of these patients (30 out of 60) would be eligible for the trial, and we are seeking to recruit at least 50% of eligible patients (n=15). The Glomerulonephritis Clinic at Vancouver General Hospital has a larger patient population and we are seeking to recruit 10 patients from that site.

The total sample size of 25 participants is supported by a sample size calculation for the feasibility metric of retention of participants in the trial. The progression criterion for this outcome is 80%. Assuming 90% of participants complete the 6-month study duration, a total of 26 participants would be needed to provide a one-sided 95% confidence interval of 10% (i.e. a lower bound estimate of 80%).

For a definitive trial, a sample size of 186 patients would provide 80% power to detect a between-group mean difference in systolic BP of 7 mmHg (a more conservative effect size compared to TASMIN-SR) assuming a standard deviation of 17 mmHg.

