	
 
Proteinuria > 0.5 g/day quantified from 24-hour urine collection or urine protein:creatinine ratio >50 mg/mmol or urine albumin:creatinine ratio >30 mg/mmol
 
Clinic systolic BP >130 mmHg or diastolic BP >85 mmHg (automated office BP measurement)
 
Willing to self-manage BP
 

Exclusion criteria	Any of the following:
	Currently receiving immunosuppression or in need of urgent start immunosuppression (e.g., rapidly progressive glomerulonephritis or nephrotic syndrome)
	
 
Kidney failure defined by the need for dialysis, kidney transplantation or eGFR <15 mL/min
 

	Recent (within 3 months) history of acute myocardial infarction or stroke
	Heart failure with reduced ejection fraction
	Concomitant diabetic nephropathy on kidney biopsy
	Pregnancy (or actively planning a pregnancy) or breastfeeding
	Life expectancy <12 months
	Allergy or intolerance to both an angiotensin converting enzyme
	inhibitor and angiotensin II receptor blocker
	Severe hypertension (>180/100 mmHg)
Treatments	Intervention arm (study treatment)
	Self-management of BP including self-monitoring of home BP values and self-titration of medications according to a pre-specified individualized
	treatment plan
	Control arm
	Usual management of BP and anti-hypertensive therapy by a physician at regularly scheduled clinic visits
Sample size pilot trial	Target recruitment: 25 patients over 2 years across three sites (The Ottawa Hospital Glomerulonephritis Clinic and the Glomerulonephritis Clinic in Vancouver General Hospital and St. Paul's Hospital, Vancouver)
	Justification: The target sample size is primarily based on the incidence of
	IgA nephropathy and the anticipated recruitment rate from the clinic. We
	will seek to recruit newly diagnosed patients but will also include prevalent
	patients at each site. The target sample size should be sufficient to address
	practical questions regarding the feasibility of conducting a larger clinical
	trial with respect to recruitment, ease of implementation of the intervention,
	and collection of efficacy and safety outcomes. The total sample size of 25
	participants is further supported by a sample size calculation for the
	participanto is further supported by a sample size calculation for the

	feasibility metric of retention of participants in the trial. The progression criterion for this outcome is 80%. Assuming 90% of participants complete

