# 3. Outcomes

# 3.1 Primary outcome

The primary outcome of the pilot trial will be feasibility defined as achieving target threshold for both recruitment and study completion. The study protocol will be revised based on adherence metrics and participant feedback as detailed below:

- 1. The probability of successful recruitment will be calculated as the percentage of eligible participants who are randomized. A threshold of >50% will be required for progression to a full-scale trial.
- 2. The probability of retention will be calculated as the percentage of randomized patients who complete the study. A threshold of >80% will be sought for progression to a full-scale trial.
- 3. Adherence to the self-management protocol will be quantified for each patient in the intervention group using the median number of recorded home BP readings per measurement week. Adherence will be further explored from participant feedback in longitudinal diary entries and a semi-structured interview. Fidelity of the intervention will also be explored retrospectively by comparing the submitted BP readings to the BP readings downloaded from the machine at the end of the study period. There is no progression criterion for adherence but the study protocol for a future full-scale trial will be refined based on these factors.

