# 6. Participant withdrawal and study discontinuation

# 6.1 Withdrawal of participants

Study participants will be followed until either the final study visit at 26 weeks. A participant may withdraw consent from the study at any time and for any reason. If a participant withdraws consent, they will be withdrawn from the trial. Participants will be assured that their withdrawal from the trial will not in any way affect the on-going management of their kidney condition (as would have been done had the patient not entered the study). The decision of an investigator to withdraw a study subject will be based on any or all of the following:

- i) Any clinical adverse event, safety concerns, laboratory abnormality, or other medical condition or situation occurs such that continued participation in the study would not be in the best interest of the participant
- ii) It is in the participant's best interest according to the Investigator's clinical judgment
- iii) The participant meets an exclusion criterion (either newly developed or not previously recognised) that precludes further study participation
- iv) The study is prematurely terminated

If a participant withdraws consent for further study follow-up procedures and assessments, every effort will be made to continue to follow the participant for their safety and vital status outcomes. Consent for collection of any adverse events as well as their clinical and biological data will be sought by the research team. The participant will be asked if they wish to:

- i) Withdraw from study intervention/treatment only and agree to be followed at study visits as stipulated in the protocol/consent form; OR
- ii) Withdraw from study intervention/treatment and permit follow-up by phone or review of clinic/hospital records for data collection and vital status; OR

- iii) Withdraw from study intervention/treatment and decline further contact however permit data obtained to date to be included in the analysis; OR
- iv) Withdraw from study intervention/treatment, decline further contact and access to personal health information and indicate data collected to date cannot be used in the final analysis.

Subjects who are withdrawn will not be replaced. Source documents will not be destroyed until completion of the long-term storage period.

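### The 80% lower bound for retention depends on an unnamed normal approximation that is optimistic at 25 participants, is tied to 26 rather than 25, and plays no part in the progression rule

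*Protocol*

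**What the plan says.** The synopsis sets the target: "Target recruitment: 25 patients over 2 years across three sites". It rests this mainly on disease incidence and the expected recruitment rate, and adds the retention calculation as further support.

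Section 12.1 gives the recruitment arithmetic and then states: "The total sample size of 25 participants is supported by a sample size calculation for the feasibility metric of retention of participants in the trial". It continues: "The progression criterion for this outcome is 80" per cent. Then, "Assuming 90% of participants complete the 6-month study duration", it says that "a total of 26 participants would be needed to provide a one-sided 95% confidence interval of 10% (i.e. a lower bound estimate of 80" per cent. No interval method is named. The synopsis repeats the calculation.

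The decision rule is in section 3.1 and in the synopsis row on the pilot analysis. Retention is the percentage of randomized patients who complete the study, and "A threshold of >80% will be sought for progression to a full-scale trial". No confidence bound is mentioned there. The hypothesis in section 2.1 words the same threshold as 80% or more.

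**The concern.** Three things do not fit together.

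- The text supports 25 with a calculation that it says requires 26.
- With 25 participants and 90% completion, only about 2.5 dropouts are expected. The normal approximation is poor there, and better intervals put the lower bound several points below 80%.
- Section 12.1 names 80% as the progression criterion and then justifies the sample size by a lower bound equal to that same 80%. The rule in section 3.1 does not use a lower bound.

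Retention is one of the two criteria that decide whether a full-scale trial goes ahead. If the stated precision is optimistic and is not the quantity used for the decision, readers cannot tell how much a pass would show. The two wordings of the threshold add to this, because 20 of 25 is exactly 80%.

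**Working it through.** **Inputs.** From section 12.1: n = 25 planned, 26 stated as needed, assumed retention p = 0.90, one-sided 95% confidence, distance to the bound d = 0.10. From section 3.1: pass if the observed percentage is above 80%. From section 2.1: 80% or more. The one-sided normal quantile is z = 1.645.

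**1. Reproducing the plan's figure (Wald).**
- n = z²·p(1−p)/d² = 1.645² × 0.9 × 0.1 / 0.1² = 24.35, so 25.
- Bound at n = 25: 0.9 − 1.645 × √(0.09/25) = 80.1%.
- Bound at n = 26: 0.9 − 1.645 × √(0.09/26) = 80.3%.

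The stated result is therefore reproduced to within one participant, and by this formula 25 is enough. Using a t quantile with the same standard error gives 79.95% at 26, which rounds to 80%. Other methods need clearly more: 34 for Wald with continuity correction, 35 for two-sided Wald, 40 for Jeffreys, 44 for Wilson, 46 for Agresti-Coull and 50 for exact (Clopper-Pearson).

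**2. How good the approximation is here.** At n = 25 the actual coverage of the nominal 95% one-sided Wald bound is 92.8% when true retention is 90%. A Wald bound of 80% or more needs 23 of 25. If true retention is 80%, that happens with probability 9.8%, so coverage there is 100 − 9.8 = 90.2%.

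**3. The bound at 90% retention by better methods.**
- Wilson, n = 25: centre (0.9 + 2.706/50)/(1 + 2.706/25) = 0.861; half-width 1.645 × √(0.09/25 + 2.706/2500)/(1 + 2.706/25) = 0.102; bound 75.9%.
- Exact, n = 25: the 5% quantile of Beta(x, n − x + 1) at x = 22.5; bound 74.3%.
- At n = 26: 76.3% (Wilson) and 74.7% (exact).

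90% of 25 is 22.5 completers, which cannot occur. One-sided 95% lower bounds at attainable counts are:

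| Completers of 25 | Observed | Wald | Wilson | Exact |
|---|---|---|---|---|
| 20 | 80% | 66.8% | 64.2% | 62.5% |
| 21 | 84% | 71.9% | 68.8% | 67.0% |
| 22 | 88% | 77.3% | 73.5% | 71.8% |
| 23 | 92% | 83.1% | 78.5% | 76.9% |
| 24 | 96% | 89.6% | 83.9% | 82.4% |

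By Wilson or exact, a bound of 80% needs 24 of 25. If true retention is 90%, the chance of that is 27%. By Wald it needs 23 of 25, with chance 54%.

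**4. The rule as written.** Above 80% of 25 means at least 21 completers; 80% or more means at least 20. Pass probabilities are binomial tails with n = 25:

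| True retention | Above 80% (≥21) | 80% or more (≥20) |
|---|---|---|
| 90% | 90% | 97% |
| 80% | 42% | 62% |
| 75% | 21% | 38% |
| 70% | 9% | 19% |

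A bare pass under either wording has a lower bound below 80% by all three methods.

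**The case against.** The strongest reply is that nothing has been miscalculated. The usual normal approximation gives 25 and a bound of 80.1%, and one participant moves that bound by only 0.2 points. This stands. A reader might infer that the 80% is an arithmetic error; it is not. It is an optimistic approximation by an unnamed method, and 25 against 26 is a small slip of wording.

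A second reply is that the sample size does not depend on this calculation. That also stands. Section 12.1 derives 25 from recruitment: 30 diagnoses a year × 2 years = 60, half eligible = 30, half of those recruited = 15, plus 10 from Vancouver. The synopsis calls this the primary basis. A reader might take the retention calculation as the only quantitative support, but the documents say otherwise.

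Third, planning for precision and deciding on a point estimate is legitimate in a feasibility pilot. A reader might infer from section 12.1 that a pass would demonstrate at least 80% retention with 95% confidence. No section says so: the calculation is conditional on 90% completion, and section 3.1 plainly uses the observed percentage, with a threshold that is sought rather than required. What remains is that the criterion and the bound share the figure of 80% and stand side by side with nothing to separate them.

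Finally, the choice of interval may be left to a statistical analysis plan that is not shown. But the protocol itself states the numerical bound, so that figure can be judged here.

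**Conclusion.** The point holds as a should-fix. The protocol supports 25 with a calculation stated to need 26. Its 80% bound comes from a normal approximation that is about 4 points above Wilson (75.9%) and about 6 points above exact (74.3%) at 90% retention. The bound is also not the quantity on which progression is decided: 21 of 25 passes with an exact lower bound of 67.0%, and the rule passes with probability 42% when true retention is 80%. The two threshold wordings differ by one completer, which moves that probability to 62%.

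These figures assume 25 randomized participants, all counted in the denominator as section 3.1 defines it, and independent completion with a common probability. The finding that a bare pass has a bound below 80% does not depend on which of the Wald, Wilson or exact intervals is used. The sample size of 25 is not called into question.

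**What to change.** No additional enrolment is needed. Reaching the stated bound at 90% retention would take about 44 participants (Wilson) or 50 (exact), but the sample size does not rest on it.

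1. In section 12.1 and the synopsis, replace the sentence on 26 participants and 80% with the one-sided 95% lower bound for 25 participants at 90% retention by a named method: about 74% (exact) or 76% (Wilson).
2. State there that progression is decided on the observed percentage, not on the bound.
3. Choose one threshold wording and use it in section 2.1, section 3.1 and the synopsis. Give the matching count for 25: at least 21 if above 80%, at least 20 if 80% or more.
4. State the pass probabilities of the chosen rule at true retention of 90%, 80%, 75% and 70%: 90%, 42%, 21% and 9% for above 80%, or 97%, 62%, 38% and 19% for 80% or more. Recompute them if the number randomized is not 25.
5. Report the exact or Wilson interval with the observed retention.

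The cost is a few sentences of protocol wording. The downside is that the stated precision becomes less favourable.

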# 12.2 Efficacy analysis

The between-group difference in mean systolic ambulatory BP will be the primary outcome in a future full-scale trial. In an exploratory analysis from this pilot trial, this outcome will be evaluated using mixed models adjusting for baseline BP, sex, and site (as a random effect). The proportional change in proteinuria across study visits will be analyzed using a ratio of geometric least squared means, as done previously.

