	the 6-month study duration, a total of 26 participants would be needed to
	provide a one-sided 95% confidence interval of 10% (i.e. a lower bound
	estimate of 80%).
Expected	The pilot trial will ensure the feasibility of the full-scale trial for recruitment
outcomes from	of patients and adherence to the trial protocol. Participants in the self-
pilot trial	management arm will have a positive experience and will perceive the
	intervention as sustainable in the longer term.
Sample size	For a definitive trial, a sample size of 186 patients would provide 80%
estimation for full-	power to detect a mean between-group difference in systolic BP of 7
scale trial	mmHg (a more conservative effect size compared to previous studies)
	assuming a standard deviation of 17 mmHg.
Analysis for pilot	Feasibility will be defined as achieving target thresholds for both
trial	recruitment and retention. The protocol will be refined based on metrics of
	adherence to the intervention as detailed below:
	The probability of successful recruitment will be calculated as the
	percentage of eligible participants who are randomized. A threshold of
	>50% will be required for progression to a full-scale trial.
	2. The probability of retention will be calculated as the percentage of
	randomized patients who complete the study. A threshold of >80% will be
	sought for progression to a full-scale trial.
	3. Adherence to the self-management protocol will be quantified for each
	participant using the median number of recorded home BP readings per
	measurement week and further explored in participant diaries and
	interviews. There is no threshold for progression to a full-scale trial;
	however, the protocol will be refined based on these factors.
Analysis for full-	The between-group difference in mean systolic BP will be the primary
scale trial	outcome in a future full-scale trial. This will be evaluated using mixed
	models adjusting for baseline BP, sex, and site (as a random effect). The
	proportional change in proteinuria across study visits will be analyzed using
	a ratio of geometric least squared means.
Study visits	Study visits will occur in-person at baseline (time of randomisation), then at
	week 12 and a final study visit at 26 weeks. Participants in the self-
	management group will have one additional visit at or close to the time of
	randomization for teaching and training.

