# 4.3 Randomization and allocation process

Randomization will be 2:1 intervention-to-control, and will be carried out with a web-based randomization system. A 2:1 allocation was chosen because there is already extensive experience of the usual care arm of the trial, and the intent is to determine the acceptability and safety profile of the intervention. The randomization website will be managed by the Data Management Services of the Ottawa Methods Centre Ottawa Hospital Research Institute. Randomization will be stratified by site (Ottawa versus Vancouver).

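### The pilot's exploratory systolic BP model treats site as random, but the stratification factor has only two levels; a fixed stratum term is a minor, nearly free improvement

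*Protocol*

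**What the plan says.** Section 12.2 (Efficacy analysis) specifies, for an exploratory analysis of the pilot, that "this outcome will be evaluated using mixed models adjusting for baseline BP, sex, and site (as a random effect".

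Section 4.3 (Randomization and allocation process) fixes the design: "Randomization will be 2:1 intervention-to-control", and "Randomization will be stratified by site (Ottawa versus Vancouver". Site is the only stratification factor.

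Section 12.1 (Sample size justification) plans 15 patients from Ottawa ("we are seeking to recruit at least 50% of eligible patients (n=15") and 10 from Vancouver ("we are seeking to recruit 10 patients from that site"). The synopsis describes recruitment of "25 patients over 2 years across three sites", two of the three being hospitals in Vancouver.

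The synopsis row on analysis of the full-scale trial gives the same covariates, with "models adjusting for baseline BP, sex, and site (as a random effect". That row concerns a later trial whose number of sites is not stated.

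**The concern.** A random effect treats the sites as draws from a population of sites and estimates the variance of that population from the data. Two levels leave 1 degree of freedom for that variance. REML then often returns exactly zero, and at zero the model is the same as one with no site term.

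An analysis should normally include the factors used to stratify randomization. Under section 12.2, whether site stays in the model depends on a very imprecise variance estimate. The choice is made in the protocol itself, so an analysis plan that follows the protocol inherits it.

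**Working it through.** **Inputs.** From the protocol: 15 Ottawa and 10 Vancouver patients (12.1), 2:1 allocation within two strata (4.3), and a model with treatment, baseline BP, sex and site (12.2). The systolic BP SD of 17 mmHg comes from the full-scale calculation in 12.1. Assumed: the size of the site difference, which the protocol does not give.

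**The protocol's own figure.** No number is stated for the site term. The one figure tied to this SD reproduces. With two-sided 5% (assumed) and 1:1 allocation, n per arm = 2 × (1.960 + 0.842)² × 17² / 7² ≈ 92.6, so 93 per arm and 186 in total.

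**Precision of a 1-df variance.** The 95% multipliers on an SD estimated from 1 df are √(1/χ²) at the 97.5th and 2.5th percentiles, that is 0.45 and 31.9. The interval spans a factor of about 70, so the estimate is practically uninformative.

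**How often the variance is zero, analytic approximation.** The REML estimate is zero when the between-site F statistic on (1, 20) df is below 1. The 20 df are 25 patients minus 5 parameters (intercept, treatment, baseline, sex, site).

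- *Site as a random draw with SD τ.* The effective size is n₀ = 25 − (15² + 10²)/25 = 12. The probability is P(F(1,20) < 1/(1 + 12τ²/17²)).
- *Site as a fixed gap g.* The noncentrality is λ = g² × (15 × 10/25)/17² = 6g²/289. The probability is P(F(1,20; λ) < 1).

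| Assumed site SD τ (mmHg) | Analytic | Simulated (1,000 trials each) |
|---|---|---|
| 0 | 67% | 67.5% |
| 2 | 63% | 62% |
| 3.4 | 58% | 61% |
| 5 | 51% | 52% |
| 8.5 | 38% | 37% |

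| Assumed site gap g (mmHg) | λ | Analytic, no dropout | Simulated, about 10% dropout |
|---|---|---|---|
| 0 | 0 | 67% | 67% |
| 5 | 0.52 | 56% | 60% |
| 10 | 2.08 | 32% | 36% |
| 15 | 4.67 | 12% | 18% |

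Dropout leaves less information on the gap, so slightly higher shares are expected in the last column.

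**Three hospitals instead of two strata.** With an assumed 15/5/5 split, the simulated shares for τ of 0, 2, 3.4, 5 and 8.5 mmHg are 63, 60, 54, 45 and 34%. A third level does not remove the problem.

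**Effect on the treatment comparison.** With SD 17 and about 10% dropout, standard errors are about 7.9 to 8.1 mmHg under either model. The two treatment estimates differ by about 0.4 mmHg on average, and coverage is about 94 to 95% for both with t quantiles. A separate simulation with SD 15 and no dropout, using t quantiles (20 df) for both, gives these coverages at gaps of 0, 5, 10 and 15 mmHg:

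- random site: 95.3, 95.2, 94.7, 94.7%
- fixed site: 95.5, 95.6, 94.9, 94.8%

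**Cost of a fixed term.** Residual df fall from 21 to 20 and the 97.5% t quantile rises from 2.080 to 2.086.

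**The case against.** The strongest objection is that nothing in the pilot turns on this. Section 3.2 makes efficacy exploratory only, and section 3.1 bases progression on recruitment and retention. Stratified allocation makes treatment nearly orthogonal to site, so losing the site term hardly moves the estimate. The term also drops out mainly when the observed site difference is small: the zero share falls to 18% at a 15 mmHg gap. All of this stands, and it sets the weight of the point.

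Three stronger readings are tempting, and the documents do not support them.

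- *The intervals will be too narrow.* Undercoverage of the random-site model (92.5 to 94.3% in the SD 15 setting) appears when normal quantiles are used for it. Section 12.2 names no interval method, which is commonly left to the analysis plan. With t quantiles for both models the gap practically disappears.
- *The site variance cannot be estimated at all.* An estimate on 1 df formally exists. It is unreliable, not undefined.
- *Two strata and three sites contradict each other.* Section 4.1 and the synopsis list the same three hospitals, two of them in Vancouver, and section 4.3 groups them into two strata. That is consistent.

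The objection does not justify the random term. With two levels it offers no advantage over a fixed indicator, which always keeps the stratification factor.

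**Conclusion.** The point holds as a minor one. The protocol chooses a model that does not suit its own two-level stratification. Under assumed site gaps of 0 to 10 mmHg, with SD 17 and 15 plus 10 patients, the site variance would be estimated as exactly zero in roughly 35 to 67% of pilots, and the stratification factor would then be lost from the model. The range depends on the assumed gap. The effect on the treatment estimate, its standard error and coverage is small, and no pilot conclusion is likely to change.

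A reader might infer that the full-scale model is wrong too. The protocol does not support that: the number of full-scale sites is not stated, and a random site effect is reasonable with many sites. It would matter more there only if the same few sites were kept.

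**What to change.** In section 12.2 only, replace the random site term with a fixed effect for the randomization stratum (Ottawa or Vancouver). This is one line of wording. It costs one residual degree of freedom and leaves the sample size unchanged.

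Leave the full-scale model in the synopsis as it is, or add that its random site effect applies if that trial has many sites.
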